### **Design of the study**

In a randomized control trial (RCT), participants are allocated randomly between intervention and control groups to compare the treatments, which enables statistical control over the influences imparted by the aforementioned treatments. In the present study, the policemen who satisfy our eligibility criteria and willing to consent to participate in our study will be enrolled, grouped randomly in intervention and control groups, and assessed for the dependent variables of the study before and after the Integrated Yoga intervention period.

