### **Project summary:**

Policemen recruited in the Chandigarh police who take care of the safety of VIPs most likely suffer from chronic stress, as they need to be vigilant round the clock. Since chronic stress has been shown to be responsible for multiple molecular changes at both the genomic and epigenomic levels, it can lead to various diseases like hypertension, diabetes and even cancer. Further, it has been shown that deregulation in DNA Damage Response (DDR) and DNA repair pathways is responsible for cancer. Though it is well known that yoga relieves stress and anxiety, literature lacks in studies that focus onto assessing the effect of yoga on DDR and DNA repair pathways at the molecular level. In the present study, we propose to investigate the role of yoga in modulating DDR and repair. For this, personnel of Chandigarh police who need to be extra vigilant could be the ideal cohorts. A sample size of around 230 security guards from Chandigarh police shall be recruited in the study with their consent, upon screening them for mild or severe stress on Cohen's Perceived Stress scale. 10 ml of blood will be withdrawn from the participants followed by separation of serum, plasma and WBCs from these subjects. Biochemical assays to measure the levels of cortisol (stress marker) will be performed and analyzed. This study proposes to analyze DDR markers like  $\gamma$ H2AX, 53BP1, and ATM and the extent of damage in WBCs using comet and DNA repair assays. Post the baseline assessments, they will undergo Yoga intervention for a period of 3 months, and at the end of three months, they will be assessed again on the same parameters. The baseline and post intervention results will be compared for discussion and conclusion. This study will help us to understand the effect of yoga in maintaining genomic integrity and stability at the molecular level and can assist the Department of Chandigarh police in designing strategies to improve the overall well being of policemen.

**Key words:** Yoga exercises, DNA damage response (DDR), DNA double-strand break (DSB), DNA double-strand break repair (DSBR), Cancer

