### Methodology

Recruitment of individuals: Department of Police, Chandigarh has agreed to help us on this aspect. Policemen working for Chandigarh Police will be chosen based on the inclusion and exclusion criteria.

Subjects: Those security guards (age: >20 and <60) who are willing to consent to participate in this study will be screened for moderate and higher stress on Cohen's PSS, according to inclusion criteria and randomly divided between Intervention (Yoga Group) and Control Group.

Sample Size: The sample size of 206 was calculated for 99% confidence level (reliability coefficient = 2.58), at the alpha level of 0.05, a power of 0.95, and a relative precision of 0.2, derived from a pilot study done on breast cancer patients and yoga practitioners (Ram et al, 2013). Assuming a 10% drop out rate, a total of 229 subjects will be recruited.

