**Total duration in weeks/months for yoga therapy: 3 months (13 Weeks: 5 days a week)**

### **Time schedule of activities giving milestones**

#### First year:

- A. Recruit policemen and get them to fill a questionnaire in order to identify most stressed individuals.
- B. Obtain blood samples, isolate PBMCs, serum and plasma. Biochemical analysis to test for cortisol levels will be performed.
- C. The subjects will be given yoga training for 3 months along with studying DNA damage response and repair using comet assay, immunofluorescence and real-time PCR.
- D. Follow up of the subjects to ensure compliance for yoga protocol.

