Date: February 29, 2020

NCT number: Not

Available

Official Project Title

Investigating the Role of Yoga in Alleviating
Chromosomal Translocations in Security Guards
of Chandigarh Police Who Are Responsible for
the Safety of VIPs

Statistical Analysis Plan (SAP)

1. Introduction

This Statistical Analysis Plan (SAP) outlines the planned analyses for the study titled “Investigating the Role of Yoga in Alleviating Chromosomal Translocations in Security Guards of Chandigarh Police Who Are Responsible for the Safety of VIPs”. It defines the methods for analyzing study endpoints, including descriptive, inferential, and correlation analyses.

2. Objectives and Endpoints

1. Analysis of molecular markers related to DNA damage response and repair before and after the practice of yoga on Chandigarh Police.
2. To examine the molecular mechanism by which yoga may modulate DNA damage response and repair.

3. Analysis Populations

- **Full Analysis Set (FAS):** All participants meeting eligibility criteria and providing baseline and outcome data.
- **Per-Protocol Set (PPS):** Subset of participants completing the study without major protocol deviations.

4. General Statistical Considerations

- All analyses will be conducted using **GraphPad Prism v8.0.2** and **JASP v0.19.3**.
- Two-sided significance level of $\alpha = 0.05$ will be applied.

- Adjusted p-values from post hoc tests will also use the **0.05 threshold** for significance.
- Continuous variables will be summarized with **mean \pm SD** (if normally distributed) or **median with interquartile range** (if non-normal).
- Categorical variables will be summarized as **frequencies and percentages**.

5. Assessment of Assumptions

- **Normality:** Assessed using the **Shapiro-Wilk test**.
- **Homogeneity of variance (ANOVA assumption):** Checked using **Levene's test**.

6. Statistical Methods

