6.3 Correlation Analyses

- **Normally distributed data:** Pearson's correlation coefficient.
- **Non-normal data:** Spearman's rank correlation coefficient.

7. Handling of Missing Data

- Data will be analyzed as observed (complete case analysis).
- No imputation will be performed unless otherwise specified in the protocol.

8. Interim and Sensitivity Analyses

- No interim analyses are planned.
- Sensitivity analyses may be conducted to confirm robustness of results (e.g., excluding participants with protocol deviations).

9. Reporting

- Results will be presented in accordance with **CONSORT/CONSORT-Extension guidelines**.
- Statistical outputs will include effect sizes, 95% confidence intervals, and exact p-values.

Principal Investigator

[name]

Additional Professor

Department of Experimental Medicine and Biotechnology

PGIMER, Chandigarh

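### Nothing in the readable plan requires the day-0 measurements to be finished before guards learn their arm, and the Full Analysis Set drops any randomised guard who lacks them

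*Protocol*

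**What the plan says.** **Order of steps.** The protocol, Design of the study, says eligible and consenting guards are enrolled, then "grouped randomly in intervention and control groups, and assessed for the dependent variables of the study before and after the Integrated Yoga intervention period". The Subjects paragraph under Methodology says guards are "screened for moderate and higher stress on Cohen's PSS, according to inclusion criteria and randomly divided between Intervention (Yoga Group) and Control Group"; it does not mention the blood draw or vital signs. The Project summary places baseline relative to yoga only: "Post the baseline assessments, they will undergo Yoga intervention for a period of 3 months". The first-year milestones list a stress questionnaire, then "Obtain blood samples, isolate PBMCs, serum and plasma", then yoga training, and do not mention randomisation. The time line under Variables labels the first measurements as day 0 without tying that day to allocation.

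**Who is analysed.** SAP section 3 defines the FAS as "All participants meeting eligibility criteria and providing baseline and outcome data". Section 7 plans complete-case analysis and adds: "No imputation will be performed unless otherwise specified in the protocol". The protocol specifies no imputation. The one sensitivity analysis given as an example in section 8 removes further participants and brings none back.

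**The concern.** Guards cannot be kept unaware of attending yoga five days a week for 13 weeks. If they are told their arm before day 0, two things can happen.

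- **Differential loss.** A guard disappointed with the control arm, or unwilling to take up yoga, may decline the 10 ml draw. With no baseline, that guard is outside the FAS although randomised. If such refusals differ between arms in number or in kind, the analysed groups are no longer the groups that randomisation formed. This bears on cortisol, the DNA damage response markers, the comet assay, translocations and telomere length, which all come from blood.
- **Expectation effects.** Blood pressure and resting heart rate at day 0 may shift with knowledge of the arm. SAP section 6.1 allows paired tests, so baseline values can enter the results directly.

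Refusals that occur before randomisation do neither: they reduce the number randomised but cannot unbalance the arms.

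**Working it through.** **1. The passages side by side**

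| Place | Says about order | Places randomisation against the day-0 draw? |
|---|---|---|
| Protocol, Design of the study | Enrol, group randomly, assess before and after yoga | By word order only |
| Protocol, Methodology (Subjects) | Stress screening, then random division | No; draw not mentioned |
| Protocol, Project summary | Screening, blood, then yoga | No; randomisation not mentioned |
| Protocol, first-year milestones | Questionnaire, blood, then yoga | No; randomisation not mentioned |
| Protocol, Variables (time line) | Day 0 and 3 months | No; day 0 not defined against allocation |

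No row completes baseline before allocation, and none says when guards learn their arm. The stress score used for screening does precede randomisation. The exposure is therefore mainly in the blood measures and vital signs.

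**2. The plan's own figure**

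The Sample Size paragraph gives 206, a 10% dropout and 229 recruited: 206 / (1 − 0.10) = 228.9, rounded up to 229. This reproduces. The allowance is 229 − 206 = 23 guards.

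**3. What a loss of given size would do**

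The documents give no refusal rate, so every input in this step except the totals is assumed. Take equal allocation (115 and 114). Suppose a fraction f of the 115 leaves before day 0, none leave the other arm, and the leavers' mean outcome differs from their whole arm's mean by k SD. The retained mean then moves by

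shift = k × f / (1 − f).

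With no true yoga effect, the standard error of the difference in SD units is √(1/n₁ + 1/n₂). The chance of a significant two-sided 5% result is 1 − Φ(1.96 − shift/SE) + Φ(−1.96 − shift/SE).

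| Lost of 115 | f | Analysed | Shift, k = 0.25 / 0.5 / 1 | Error rate, k = 0.25 / 0.5 / 1 |
|---|---|---|---|---|
| 6 | 5.2% | 109 v 114 | 0.014 / 0.028 / 0.055 SD | 5.1% / 5.5% / 7.0% |
| 12 | 10.4% | 103 v 114 | 0.029 / 0.058 / 0.117 SD | 5.5% / 7.1% / 13.7% |
| 23 | 20.0% | 92 v 114 | 0.062 / 0.125 / 0.250 SD | 7.3% / 14.5% / 43.0% |

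Worked case, last row, k = 0.5: shift = 0.5 × 0.20/0.80 = 0.125; SE = √(1/92 + 1/114) = 0.140; error rate 14.5%. That row puts the whole dropout allowance into one arm before day 0 and is an extreme.

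For scale, 103 per arm at two-sided alpha 0.05 and power 0.95 detects (1.960 + 1.645) × √(2/103) = 0.50 SD. The shifts run from about 3% to 50% of that difference.

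**4. After the change**

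If guards are randomised only once day 0 is complete, f for this route is zero. Losses between day 0 and 3 months are unaffected.

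**The case against.** The strongest reply is that the order is unspecified, not wrong. The design sentence is general; its "before" refers to the yoga period, and it covers both assessments in one clause, so it is compatible with baseline taken first. The Project summary and the milestones fit that order too. The work plan figure and the content of the CONSORT flow chart are not in the available text, and they are where the order would most likely be shown. Disclosure before day 0 is an inference. All of this stands. A reader might infer that the protocol fixes randomisation before baseline, or that guards will know their arm at the draw; the documents support neither.

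Three further limits also stand. A reader might fear bias in baseline self-reported stress, but the screening score is collected before random division (whether it also serves as the pre-intervention score is not stated). A reader might object to adjusting for a contaminated baseline, but the SAP plans no baseline-adjusted model; the exposure is through paired or change analyses. And knowing the arm has no evident way to alter day-0 comet, translocation or telomere results, so for those the risk is loss of guards only.

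The SAP's commitment to CONSORT reporting would make losses by arm visible. It would not restore the lost guards to the analysis.

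What the reply does not remove is that no readable text protects the day-0 measurements, and that the FAS rule turns a missing baseline into an exclusion after randomisation.

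**Conclusion.** The point holds as a gap in protection, not as a demonstrated error of sequence. As the readable text stands, a site could randomise, disclose the arm and then take the day-0 sample without departing from the protocol. The SAP would then remove any guard who declined. The consequence is possible differential loss of the blood-based measures and possible expectation effects on blood pressure and heart rate.

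Its size cannot be stated from the documents. Under the assumed one-sided losses above it runs from negligible (5.1% error rate) to serious (43% in the extreme case), and it is zero if staff already measure first. The change is worth making because it costs almost nothing.

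The FAS wording needs attention in either case. It also requires outcome data, and exclusion criterion iv removes guards who do not comply with yoga from that arm only. Both act after randomisation, and taking baseline first cures neither.

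**What to change.** 1. In the protocol (Methodology, Subjects; and Design of the study), state the order: consent, screening, all day-0 assessments including blood pressure, heart rate and the 10 ml draw, then randomisation and disclosure of the arm, then the first yoga session. Say that guards who do not complete day 0 are not randomised. If the work plan or flow chart already shows this order, the text should match it.
2. In SAP section 3, define the FAS as all randomised guards in their assigned arm, without the condition on baseline and outcome data. Reconcile exclusion criterion iv with that definition.
3. In SAP section 7, state how missing baseline and outcome values are handled; otherwise the complete-case rule brings the same exclusions back.

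**Cost:** wording and the order of two steps, with the same visits and procedures, plus a short missing-data paragraph. A few guards may give a day-0 sample and then not be randomised.

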### **Variables**

- Socio-demographic details – age, diet, alcohol consumption, etc.
- Evaluation of stress level on Cohen's Perceived Stress Scale (pre and post intervention) (Cohen, Kamarck & Mermelstein, 1983)
- Evaluation of stress level using vital parameters: Blood pressure and resting heart rate of participants will be recorded pre and post intervention.

- Evaluation of stress level using molecular parameters: (pre and post intervention) 10 ml of blood will be withdrawn from the subjects by trained phlebotomists, and coded. WBCs and plasma will be separated using standard protocols and stored at -80°C. Plasma will be utilized to assess the levels of cortisol.
- Assessment of chromosomal translocations: (pre and post intervention) Genomic DNA will be extracted from WBCs isolated, and tested for chromosomal translocations using PCR assay. Isolated genomic DNA will be subjected to nested PCR using primers specifically designed to check for t(14;18) and t(11;14) translocations.
- Assessment of DDR and DNA repair:
- *Immunofluorescence*: Isolated PBMCs will be subjected to DDR analysis by immunofluorescence. For this, these cells will be fixed and stained with various DDR markers like γH2AX, 53BP1, pATM.
- *Gene expression analysis*: Total RNA will be isolated from these cells; cDNA will be synthesized and the expression of following DDR and DNA repair genes will be performed using real-time PCR: RAD51, MRE11, RAD50, NBS1, KU70, LIGASE IV, PARP1
- *Comet assay*: Cells will be used to perform both the neutral as well as alkaline comet assay to assess for the number of single- and double-strand breaks.
- Telomeric length: Relative telomere length (TL) using quantitative polymerase chain reaction (qPCR) will be performed on genomic DNA isolated from control and group blood samples and will be compared.

Time Line for experiments:

S.No.	Experiments	Time point
1.	Cortisol levels	0 day
2.	DDR: Immunofluorescence for γH2AX, 53BP1, and ATM.  Gene expression analysis for KU70, LIGASE IV, RAD51,	0 day

	PARP1, MRE11, RAD50, NBS1	
3.	Nested PCR for Chromosomal Translocations	0 day
4.	DNA repair: Comet assay	0 day
5.	Cortisol levels	3 months
6.	DDR: Immunofluorescence for $\gamma$ H2AX, 53BP1, and ATM.  Gene expression analysis for KU70, LIGASE IV, RAD51,  PARP1, MRE11, RAD50, NBS1	3 months
7.	Nested PCR for Chromosomal Translocations	3 months
8.	DNA repair: Comet assay	3 months

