## **Objectives**

1. Analysis of molecular markers related to DNA damage response and repair before and after the practice of yoga on Chandigarh Police
2. To examine the molecular mechanism by which yoga may modulate DNA damage response and repair.

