### Flow Chart 3: Allocation of Sample Size According to Consort Guidelines

### *Inclusion criteria*

- i. Guards scoring more than 15 points on Cohen's scale. Once these subjects' consent to enroll, each one of them will be coded to maintain anonymity.
- ii. Both males and female guards of age 20 to 60 years.

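### The schedule points to assaying day-0 and 3-month samples in separate runs with no stated masking of scorers, so the before/after contrast of Objective 1 cannot separate assay drift from a yoga effect

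*Protocol*

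**What the plan says.** **Timing of assays.** In Protocol, Variables, the time line for experiments lists assays rather than blood draws. Cortisol, the damage-response panel, nested PCR and the comet assay each appear twice, for example "DNA repair: Comet assay 0 day" and later "DNA repair: Comet assay 3 months". Telomere length is among the variables but not in this table. In the first-year schedule, step B puts the cortisol analysis with the blood collection, and step C reads "The subjects will be given yoga training for 3 months along with studying DNA damage response and repair", by comet, immunofluorescence and real-time PCR. The second-year schedule adds a further group.

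**Storage and coding.** Plasma and WBCs are to be "separated using standard protocols and stored at -80°C". No storage is stated for RNA, cDNA, slides or images, or specifically for the cells used in immunofluorescence and comet. Under the inclusion criteria, consenting guards are enrolled and "each one of them will be coded to maintain anonymity". The Variables section also says that the blood is coded, without giving a purpose. Neither document mentions allocation of samples to runs, run controls or masked scoring.

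**The contrast.** Objective 1 is "Analysis of molecular markers related to DNA damage response and repair before and after the practice of yoga on Chandigarh Police", and SAP section 2 repeats it. The project summary says: "The baseline and post intervention results will be compared for discussion and conclusion". Protocol, Design of the study, does specify a randomised control group assessed at both times. SAP section 6.1 allows paired or unpaired tests and names no between-arm test of change.

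**The concern.** If all baseline samples are assayed before any 3-month sample exists, run and visit coincide in the before/after contrast. A new reagent lot, a recalibration or a change in staining intensity then looks the same as an effect of three months of yoga, and the yoga arm alone cannot tell the two apart. Foci and comet scoring also involve judgement, and a scorer who knows the visit or the arm can add bias in the expected direction.

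At stake is the conclusion on the run-based laboratory markers. Perceived stress, blood pressure and heart rate are not affected. Nested PCR looks for specific translocations, so a shift measured in SD units does not carry over to it directly.

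**Working it through.** **Inputs from the documents.** 206 evaluable guards, 10% dropout and 229 recruited (Protocol, Sample Size); two-sided alpha 0.05 (SAP section 4). The only related stated figure reproduces: 206 / 0.9 = 228.9, rounded up to 229. The documents give no figure for drift or run variation.

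**Assumed inputs.** A 1:1 split, so 206 / 2 = 103 per arm (the allocation ratio is not stated); no true change; change scaled to SD 1; drift *g* in units of that SD.

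**1. Within-arm paired test, one common shift for all pairs.** The statistic is noncentral *t* with 102 degrees of freedom, noncentrality *g* × √103 and critical value 1.983.

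| Shift *g* | Noncentrality | False-positive rate |
|---|---|---|
| 0 | 0 | 5% |
| 0.1 | 1.01 | 17.1% |
| 0.2 | 2.03 | 52.0% |
| 0.3 | 3.04 | 85.4% |

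**2. Within-arm paired test, shifts that vary by cohort.** Suppose each of *k* equal cohorts has its own independent shift with mean 0 and SD 0.2. The mean change has variance 1/103 + 0.04/*k*. The test allows only for about (1 + 0.04(*k* − 1)/*k*)/103. The rejection rate is then approximately 2 × [1 − Φ(1.96 × √(1 + 0.04(*k* − 1)/*k*) / √(1 + 103 × 0.04/*k*))].

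| Cohorts *k* | Rejection rate |
|---|---|
| 1 | 39% |
| 2 | 26% |
| 4 | 16% |
| 10 | 9% |

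The inflation falls as runs multiply but does not vanish. The number of cohorts is also an assumption; the schedule shows only that there is more than one group.

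**3. Between-arm test of change, same drift in both arms.** The shift subtracts out, because (*g* + yoga change) − (*g* + control change) does not contain *g*. Simulation (20,000 replicates, 103 per arm) gives 4.8%, 5.2% and 4.7% for *g* = 0.1, 0.2 and 0.3.

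**4. Between-arm test, two runs differing by 0.5 SD, run unrelated to arm.** Simulated type I error is about 5%. Equal shares in each run are not needed for this.

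**5. Between-arm test, arms handled unevenly.** With the same two runs but a fixed 60/40 split in one arm and 40/60 in the other, the bias is 0.2 × 0.5 = 0.10 SD. The standard error is √(2/103) = 0.139, the noncentrality is 0.10 / 0.139 = 0.72, and the type I error is 11%. No passage says that the arms would be handled this way; the case shows what balanced runs guard against.

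**The case against.** The strongest objection is that separate runs are not stated. The column in the time line is headed as a time point and could give sampling dates, and the first-year step is a milestone rather than a run schedule. This stands in part: separate running is an inference. It is still the better-supported reading, because the rows name experiments and the schedule has assays under way during training. No text prevents it.

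Second, the trial has a randomised control arm, and one of the key questions in the protocol compares yoga practitioners with controls. Drift shared by both arms cancels in that comparison. This stands fully, and it limits the point to the within-arm contrast. It does not dispose of it, because Objective 1, the summary and the SAP objective all state the before/after contrast, and the SAP does not commit to comparing change between arms.

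A reader might go further and infer that drift also biases the between-arm comparison unless every run holds both arms in equal share. The documents do not support that: bias there needs arms handled unevenly across runs, or a scorer who knows the arm, and neither is stated. Nor do they support the inference that scorers are unmasked. The blood is coded for a purpose that is not given, so the documents are silent on masking. A third tempting inference is that storage would let every assay be paired by run. Storage is stated for plasma and WBCs only.

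Finally, plate layout is often left to laboratory procedures. That is fair for the detail, but the rules on pairing, balance and masking decide whether the stated contrast can be interpreted, and unbalanced runs or unmasked readings cannot readily be repaired at analysis.

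**Conclusion.** The point holds for the within-arm before/after contrast. Followed as written, the plan most likely assays the two visits separately, and that contrast then cannot distinguish assay drift from yoga. The size is illustrative: 17%, 52% or 85% false positives for a common shift of 0.1, 0.2 or 0.3 SD of the change, and less where shifts vary over cohorts (39% with one cohort to 9% with ten, at a shift SD of 0.2). The 1:1 split, the drift sizes, the number of cohorts and separate running itself are all assumptions. A between-arm comparison of change keeps about 5% type I error unless arms are handled unevenly or the arm is known to the scorer. The change should be made, with medium confidence, because it is cheap and has to be in place before samples are assayed.

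**What to change.** 1. Assay both visits of a guard in the same run for plasma cortisol and for the DNA assays on stored WBCs (translocation PCR, telomere length). Do the same for gene expression if RNA or cDNA is banked. Balance the two arms in each run.
2. For immunofluorescence and comet, process both arms in the same sessions. Score slides or images in random order under codes that hide the arm and, where slides or images are kept, the visit.
3. In the SAP, base the conclusion on the between-arm comparison of change and report the within-arm before/after test as descriptive. This alone removes common drift. It does not replace balanced runs or masked scoring.

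The sample size of 206 (229 recruited) does not change and no further blood is needed. The cost is plate planning, relabelling and about three months' wait for baseline results. Day-0 material will also be stored longer than 3-month material. That difference is equal in both arms but differs by visit, so it is a further reason for item 3.

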6.1 Comparisons of Two Groups

- **Normally distributed data:** Student's *t*-test (paired or unpaired as appropriate).
- **Non-normal data:** Wilcoxon matched-pairs signed rank test (paired) or Mann-Whitney test (independent).

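### For translocations, the outcome in the study title, the SAP does not say that the randomised arms are compared, and names no test for proportions and no comparison that uses the 0-day result

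*Protocol*

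**What the plan says.** **The outcome.** The SAP title names chromosomal translocations as the target. Neither objective mentions them. The protocol (Variables) describes the assay, "Isolated genomic DNA will be subjected to nested PCR using primers specifically designed to check for t(14;18) and t(11;14) translocations", and its experiment timeline places it at 0 day and 3 months.

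**The tests.** For two groups, SAP 6.1 gives Student's t-test "paired or unpaired as appropriate" or, for non-normal data, the signed-rank test when paired and the Mann-Whitney test when independent. Section 6.2 adds one-way ANOVA and Kruskal-Wallis; section 6.3 adds correlations. For categorical data, section 4 says only this: "Categorical variables will be summarized as frequencies and percentages". No test is assigned to translocations.

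**The contrast.** Two descriptions stand side by side.
- Before versus after: the protocol's Project summary says "The baseline and post intervention results will be compared for discussion and conclusion", and SAP objective 1 speaks of markers "before and after the practice of yoga on Chandigarh Police".
- Yoga versus control: the protocol's Design of the study explains that in a randomised trial "participants are allocated randomly between intervention and control groups to compare the treatments" and applies that design here. Key question (b) also asks for a comparison with controls, though for DNA repair capacity.

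**The concern.** With two randomised arms each measured twice, the tests in SAP 6.1 answer different questions. A paired test inside the yoga arm asks whether yoga participants changed. It makes no use of the controls, so a change common to everyone (assay drift, season, repeat testing) appears as an effect of yoga. An unpaired test at 3 months asks whether the arms differ. That is the randomised question, but the test ignores the 0-day result, which is scheduled for every participant. The plan does not say which one supports the conclusion, and its own descriptions of the contrast point both ways. At stake is whether a statement that yoga alleviates translocations rests on the randomisation or on a before-after change in one arm.

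**Working it through.** **Inputs.** The evaluable sample is 206 (protocol, Methodology, Sample Size). The recruitment figure reproduces: 206 / 0.9 = 228.9, rounded up to 229. The 206 cannot be checked, because the pilot values behind it are not given, but nothing below depends on it. I assume equal allocation, 206 / 2 = 103 per arm, since the readable text states no ratio. Alpha is 0.05 two-sided (SAP section 4). The outcome is taken as detected/not detected. The documents give neither prevalence nor persistence, so both are assumed and varied.

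**Example A: the paired test claims an effect that the arms do not show.** Yoga goes from 21 to 13 positive (10 lost, 2 gained); controls go from 21 to 16 (8 lost, 3 gained).
- Signed-rank in yoga: z = (10 − 2)/√12 = 2.31, p = 0.021 (exact McNemar 0.039). In controls: z = (8 − 3)/√11 = 1.51, p = 0.13.
- Unpaired at 3 months, 13 v 16 of 103: p = 0.55.
- Stratified by 0-day status. Positives: 11/21 v 13/21, observed minus expected in yoga 11 − 12 = −1. Negatives: 2/82 v 3/82, 2 − 2.5 = −0.5. The sum is −1.5 and the variance 3.853, so chi-square = 2.25/3.853 = 0.58, p = 0.44.

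**Example B: the unadjusted test misses what the stratified test finds.** Yoga as in A; controls go from 21 to 21 (2 lost, 2 gained).
- Unpaired, 13 v 21 of 103: p = 0.13.
- Stratified. Positives: 11/21 v 19/21, 11 − 15 = −4. Negatives: 2/82 v 2/82, 0. The variance is 2.195 + 0.982 = 3.177, so chi-square = 16/3.177 = 5.04, p = 0.025 (0.0496 with continuity correction).
- Mantel-Haenszel risk difference: weights 21×21/42 = 10.5 and 82×82/164 = 41, giving −4/51.5 = −7.8 points (95% CI −14.7 to −0.8).

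Example B is borderline; it illustrates the mechanism and should not be read as typical.

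**Simulation.** Let p0 be baseline prevalence and s the share of baseline-positive controls still positive at 3 months. Prevalence is held stable by a gain rate of p0(1 − s)/(1 − p0) among negatives. At s = p0 the 0-day result carries no information.

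*No yoga effect.* All 3-month positive probabilities are multiplied by 0.75 in both arms.

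| Shared fall | Paired test in yoga arm significant | Unadjusted between arms | Stratified between arms |
|---|---|---|---|
| 20% to 15% | 16% to 43%, rising with s | about 5% | about 5% |
| 10% to 7.5% | about 9% to 22% | about 5% | about 5% |

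*True halving by yoga.* Power at 0.05:

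| Control prevalence | Unadjusted | Stratified, s = p0 | s = 50% | s = 70% | s = 90% |
|---|---|---|---|---|---|
| 20% | 53% | 52% | 56% to 57% | 66% | 86% |
| 10% | 28% | 27% | 30% | 37% | 55% |

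**The case against.** The strongest reply is that the plan already implies the right comparison. The trial is randomised, key question (b) refers to controls, and SAP section 9 follows CONSORT and promises that "Statistical outputs will include effect sizes, 95% confidence intervals, and exact p-values". The before-after wording comes from a summary and an objective and is not a test rule. Much of this stands: the SAP does list unpaired tests, and it nowhere says that a within-arm test decides. But the Project summary ties the before-after comparison to the conclusion, and nothing in the SAP settles the choice.

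A second reply is that baseline adjustment is a matter of efficiency. That stands too. The unadjusted test holds its 5% error rate, and at 20% prevalence the gain from stratifying runs from −1 point with no persistence to +33 points at 90%.

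Third, the SAP assigns no test to any outcome, so translocations are not special in that respect. This is true; they matter here because the title names them.

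A reader might also infer that the PCR scoring is wholly undefined. The documents do not support that. The Variables section speaks of testing and checking for translocations, whereas for telomere length it specifies a quantitative PCR, so detected/not detected is the natural reading. Details such as replicates, or whether the two targets are combined, are missing, but that is a smaller matter. Nor is the use of rank tests on 0/1 data the problem: at 21 v 5 positive, rank and chi-square tests both give p = 0.0008.

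**Conclusion.** The concern holds in a limited form. For translocations the SAP names no test for proportions and no between-arm comparison that uses the 0-day result, and it leaves the paired or unpaired choice open while the documents describe both contrasts. The main risk is a conclusion drawn from the yoga arm alone: under the assumed shared falls, that test would be significant in about 9% to 43% of trials with no yoga effect. The secondary cost is power left unused, which may be nil and is large only if most positives persist. All these sizes rest on assumed prevalence, persistence and equal allocation.

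It would go too far to say that the plan has no between-group test, that it commits to a within-arm conclusion, or that an unadjusted between-arm test would be invalid. Where the listed tests disagree, the disagreement is significant against not significant, not a reversal of direction.

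**What to change.** Add one paragraph to SAP 6.1:
- Translocation results are read as detected/not detected.
- Conclusions rest on the randomised arms compared at 3 months, stratified by 0-day status, reported as a Mantel-Haenszel risk difference with 95% CI and the Cochran-Mantel-Haenszel test, using an exact version if positives are sparse.
- Within-arm McNemar or signed-rank tests are descriptive only.

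Holm adjustment over the two translocations is optional. If it is adopted, power should be quoted at the adjusted level. At 0.025, for a halving from 20%, stratified power is about 41%, 45%, 55% and 79% for persistence of 20%, 50%, 70% and 90%, against 42% unadjusted.

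No new data are needed, because the 0-day PCR is already scheduled. The sponsor should confirm that the software named in SAP section 4 runs the stratified analysis, or name software that does.
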